Consecutive clients/patients with documented chronic hepatitis infection (detectable HCV RNA) seen at one of the study sites that are interested in HCV treatment and fulfill inclusion/exclusion criteria will be enrolled. Each site will determine readiness for treatment. Final approval for treatment initiation and ongoing monitoring during treatment will be under the supervision of the medical provider panel led by [name].

Retrospective Study Cohort

The Electronic Medical Record of the OHSU hepatology clinic will be reviewed and patients treated for hepatitis C with Zepatier selected in a retrospective, sequential fashion, starting at the time of closure of enrollment at the two prospective sites.

Screening Data Disposition

All data collected during screening for patients not meeting inclusion criteria, or meeting exclusion criteria, will be destroyed immediately, EXCEPT for the reason for exclusion, which will be collected and saved in a de-identified manner until study completion for the purposes of establishing external validity.

Inclusion Criteria

- 1) Genotype 1b and genotype 1a without baseline NS5A resistance or Genotype 4
- 2) APRI Score <0.7; if >0.7 a Fibrosure/Fibrotest or Fibroscan score of F2 or less, plus no clinical or laboratory evidence of cirrhosis
- 3) Readiness for treatment based on ability to make >2/3 sequential office visits either prospectively or retrospectively.
- 4) Patients must be assessed to have decision-making capacity, be capable of consenting, and not be displaying evidence of overt intoxication.

Exclusion Criteria

- 1) Previously treatment for hepatitis C infection
- 2) Clinical, radiologic, or laboratory evidence of cirrhosis
- 3) Hepatocellular carcinoma, HIV or hepatitis B virus co-infection, elevated prothrombin time unrelated to anticoagulation, hemoglobin level less 11 g/dL, platelet count <150 × 10⁹ cells/L, WBC <4.0 x10³/mm³, aminotransferase levels more than 10 times the upper limit of normal, or albumin level <3.0 g/L, positive office-based pregnancy test.
- 4) Subjects taking medications that are contra-indicated to administer with Zepatier including phenytoin, carbamazepine, rifampin, St. John's Wort, and cyclosporine. Study pharmacists will assess drug interactions.
- 5) Persons under the age of 18

c. Vulnerable Populations

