- Screening, treatment interventions, and follow up are outlined below. All of the following represent standard of care interventions, with the exception of survey data collection and in-depth qualitative interviews. These interviews serve the purpose of better understanding potential barriers to successful treatment and to identify potential mitigating innovations in the care of this complicated and neglected population.

Treatment Scheme

Baseline Testing (already performed as a part of standard of care for a patient with HCV infection)

- CBC with differential, Complete Metabolic Profile, GFR, INR, HCV genotyping with NS5A resistance testing for genotype 1a, HCV RNA, HIV, pregnancy test in female of childbearing age
- APRI score or Fibrosure or Fibroscan to determine fibrosis stage. APRI score is defined as AST level in IU/L over 40 IU/L (upper limit of normal value) divided by platelet count in $10^9/L$ multiplied by 100 or.

Screening Visit

- Consent process including discussion of the consent form
- History and physical to exclude signs and symptoms of cirrhosis
- Inclusion and exclusion criteria assessed
- NS5A resistance testing for genotype 1a subjects (subjects excluded if baseline resistance present)
- Assess subject's readiness for treatment: Subjects must have established care as a primary care patient at Outside In or Old Town Clinic. They must express a desire to be treated and to adhere to all laboratory monitoring and visit requirements.
- Screen failure subjects will be linked to appropriate care within the study site or at OHSU hepatology for further management

Visit 1

- Clinic Visit
- Once enrolled, completion of validated questionnaires (see Appendix that includes additional references) that assess the subject's understanding of health, current health status, addiction and severity of addiction, social support, and degree of stigma. These assessments have been described in hepatitis C infected population.^{6,7,8}

Visit 2

- Clinic visit
- Verify the following studies/assessments are complete including CBC; INR, complete metabolic profile; GFR; genotype 1a, 1b, or 4 HCV RNA; no baseline RAVs for genotype 1a subjects
- Verify Readiness for treatment

- Verify questionnaires completed
- Pregnancy counseling

Visit 3 (Initiation of HCV treatment)

- Clinic visit
- Check in post-survey on subject well-being
- Pharmacy dispenses 2 weeks, or less if indicated* of HCV medication

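### In Exclusion 3 the number and unit of the albumin limb do not fit together, so read literally that limb excludes effectively no one

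*Combined protocol and SAP*

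**What the plan says.** Exclusion 3 in section 5b of the combined protocol and SAP is one item with many limbs. Its albumin limb reads "albumin level <3.0 g/L". The hemoglobin limb of the same item reads "hemoglobin level less 11 g/dL". Other limbs cover "elevated prothrombin time unrelated to anticoagulation", "platelet count <150 × 10⁹ cells/L", white cell count and aminotransferases.

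Advanced liver disease is also addressed outside this item. Exclusion 2 removes patients with "Clinical, radiologic, or laboratory evidence of cirrhosis". Inclusion 2 requires a low APRI score or a fibrosis stage of F2 or less, together with no evidence of cirrhosis.

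The baseline tests in section 6 are listed as "CBC with differential, Complete Metabolic Profile, GFR, INR" and further assays. Albumin is not named separately there, and no unit or reference range is given for it anywhere in the document.

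**The concern.** An eligibility limit should be usable as printed. This one is not: a limit of 3.0 in g/L lies far below any albumin value that a clinic would expect in an outpatient, so the limb cannot operate if taken literally. Someone who notices this will probably assume a slip in the unit or the number and apply something else.

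Eligibility is judged by different people at Outside In and Old Town Clinic, with final approval by a provider panel. The text gives them no way to settle which reading is meant. A departure among excluded patients would also be hard to trace later, because section 5b has their screening data destroyed and keeps only the reason for exclusion.

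What is at stake is whether one stated criterion is applied as intended and in the same way throughout.

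**Working it through.** The plan has no figure of its own to reproduce here. The check is a unit conversion followed by a sensitivity calculation.

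**Inputs from the protocol (section 5b, Exclusion 3).** Albumin limit 3.0 g/L; hemoglobin limit 11 g/dL.

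**Step 1: conversion.** 1 g/dL = 10 g/L.
- Albumin limit as printed: 3.0 / 10 = 0.30 g/dL.
- The same number taken in g/dL: 3.0 × 10 = 30 g/L.
- The two readings differ by 30 / 3.0 = 10.

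**Step 2: comparison with expected values.** Assumption, not in the documents: adult serum albumin is about 35 to 50 g/L, and marked hypoalbuminemia is about 10 to 25 g/L. Then 35 / 3.0 = 11.7 and 50 / 3.0 = 16.7, so the printed limit is about one twelfth to one seventeenth of a normal value. It also lies below the markedly low range.

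**Step 3: share of patients below the printed limit.** Assume albumin is normal with mean m and standard deviation s, both in g/L. The share is Φ((3 − m) / s), and the expected number in 50 patients is 50 times that share.

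| m | s | Share below 3 g/L | Expected in 50 |
|---|---|---|---|
| 30 | 5 | 3.3 × 10⁻⁸ | 1.7 × 10⁻⁶ |
| 30 | 7 | 5.74 × 10⁻⁵ | 0.0029 |
| 35 | 7 | 2.4 × 10⁻⁶ | 1.2 × 10⁻⁴ |
| 40 | 7 | 6.3 × 10⁻⁸ | 3.1 × 10⁻⁶ |
| 45 | 7 | 9.9 × 10⁻¹⁰ | 4.9 × 10⁻⁸ |

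The worst case is m = 30, s = 7: (3 − 30) / 7 = −3.86, a share of 0.006%. All twelve combinations of m = 30, 35, 40, 45 and s = 3, 5, 7 give this value or less.

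**Step 4: does the choice of reading matter?** For comparison only, and not as a recommended limit, the share below 30 g/L under the same assumptions is Φ((30 − m) / s). It runs from under 0.1% (m = 45, s = 3) through 2.3% (m = 40, s = 5) and 15.9% (m = 35, s = 5) to 50% (m = 30). These shares ignore the other criteria, which would already remove some of the same patients. They therefore do not estimate how many patients would be wrongly admitted.

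**Step 5: reach into the analysis.** The sample-size statement in section 8 uses 50 patients per group and SVR12 rates of 95% and 70%. The primary analysis there is a chi-squared test. Albumin enters neither.

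**The case against.** The strongest reply is that this is a probable typing slip with little consequence. Eligibility is assessed by clinicians at a screening visit, and someone comparing a laboratory report with the printed limit would probably notice the mismatch. Several other criteria cover the same ground: prothrombin time, platelets, the separate cirrhosis exclusion, the fibrosis requirement, and a history and physical examination directed at cirrhosis. A letter lost in reading the PDF also cannot be fully excluded, although g/dL survived for hemoglobin in the same sentence.

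Most of this stands, and it limits the consequence. It does not make the printed limit workable, and nothing in the document tells a reader which value was intended.

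Three stronger readings are tempting, and the documents do not support them.
- A reader might infer that screening for poor liver function has failed as a whole. Only one limb of one item is inoperative; the others still work.
- A reader might infer that an automated check would let every patient through. Section 7 describes RED Cap as a data repository and mentions no programmed eligibility logic.
- A reader might infer that the prospective and OHSU cohorts will be selected differently on liver function because of this unit. Section 5b states the requirement to meet the inclusion and exclusion criteria in the prospective paragraph. The retrospective paragraph selects Zepatier-treated patients in sequence, and section 4 adds only that they are non-cirrhotic. The criteria lists do follow both paragraphs under one heading, so whether Exclusion 3 governs the OHSU cohort is left open.

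**Conclusion.** The point holds for the albumin limb of Exclusion 3. Its number and unit are inconsistent, and read literally it excludes effectively no one: at most about 0.006% of screened patients over the range tried. The alternative reading differs tenfold. The result rests on the assumption that outpatient albumin is tens of g/L, which the documents do not state, but it does not depend on a particular mean or spread within that range.

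This is an error in an operative eligibility criterion, so it should be corrected. The practical risk is inconsistent application of one limb. The number of patients affected after all the other criteria are applied cannot be worked out from the documents. Sample size, power and the primary analysis are unaffected.

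**What to change.** Reconcile the number and unit of the albumin criterion and have the investigator confirm the intended threshold. The rest of the item cannot settle the unit, because it mixes g/dL, cells per litre, counts per mm³ and multiples of the upper limit of normal. Use the confirmed text at both prospective sites and, if the exclusion criteria are meant to govern it, in the OHSU chart selection; the protocol should say whether they do. No threshold is proposed here.

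The cost is a one-line protocol correction, plus one sentence if the scope for the OHSU cohort is clarified at the same time.

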All of our subjects enrolled prospectively will suffer from a substance abuse disorder but will only be eligible for consent/enrollment if they are assessed to have decision-making capacity at the time of consent. As such, these subjects do not meet NBAC criteria of a vulnerable population. Neither of the study sites serves subjects who are currently incarcerated, so prisoners will not be asked to consent for the study. In the event that one of our fully consented subjects becomes incarcerated during the course of treatment, arrangements will be made for Zepatier and standard-of-care laboratory monitoring to be continued while incarcerated. However, optional procedures, such as interviews and surveys, will not be continued during a subject's incarceration to avoid potential inducement to participate. Zepatier is contraindicated in pregnancy, therefore pregnant women will not be included in the study. Children are also not eligible to participate.

d. Setting.

This is a multi-site study with both prospective arms of the study operated on OHSU-affiliated but not OHSU-owned properties. Site leaders will be OHSU faculty and all other principle personnel will be OHSU-affiliated and CITI-trained in concordance with OHSU IRB requirements. All sites will be relying upon the OHSU IRB for study oversight.

Outside In Needle Exchange Program

Outside In is a Federally Qualified Health Center and a Healthcare for the Homeless clinic in Portland Oregon. Its mission is to help homeless youth and other marginalized populations move towards health and self-sufficiency. The medical clinic served as a patient centered primary care home for 6000 people in 2015 providing primary and acute care, naturopathic care in both a fixed location and from outreach medical vans throughout the metropolitan region. Roughly 50% of Outside In's primary care patients report homelessness and more than 80% of its patients are at or below the Federal Poverty Line.

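### The listed visit steps do not require a current negative pregnancy test before the first dose of a drug the protocol calls contraindicated in pregnancy

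*Combined protocol and SAP*

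**What the plan says.** - **Rule.** Section 5c (Vulnerable Populations): "Zepatier is contraindicated in pregnancy, therefore pregnant women will not be included in the study". Exclusion criterion 3 in Section 5b lists a "positive office-based pregnancy test", without saying at which visit or how recently the test is to be done.
- **Where the test is listed.** Section 6, Treatment Scheme, opens with a block headed "Baseline Testing (already performed as a part of standard of care for a patient with HCV infection". It includes a "pregnancy test in female of childbearing age". No maximum age of result is stated.
- **Screening Visit.** The relevant entry is "Inclusion and exclusion criteria assessed". No pregnancy test is listed as a procedure. For Outside In, Section 5e adds that baseline laboratory tests still missing are obtained at the screening appointment.
- **Visits 1 to 3.** Visit 1 begins "Once enrolled, completion of validated questionnaires", so subjects are enrolled by then. Visit 2 verifies a list of laboratory results and includes pregnancy counseling. Visit 3 is the start of treatment and consists of a clinic visit, a check on well-being and the first dispensing.
- **Oversight.** Section 5b: "Final approval for treatment initiation and ongoing monitoring during treatment will be under the supervision of the medical provider panel".

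**The concern.** Most baseline requirements for this trial, such as genotype, change little over the weeks before treatment. Pregnancy status is different: a correct negative result can become an exclusion within weeks. A rule that keeps pregnant women off the drug therefore needs a result that is current at first dosing, and the listed steps do not ask for one.

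At stake is subject safety. A woman could test negative at baseline, be properly enrolled, conceive before Visit 3, and receive a drug that the protocol itself says she should not have, with no listed step missed by the site.

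**Working it through.** The protocol states no figure on this point, so the check sets the eligibility rule beside the visit scheme.

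**1. Count the listed tests (Section 6).**

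| Step | Pregnancy test listed? | Related item |
|---|---|---|
| Baseline Testing | Yes, once | Headed as already done; no maximum age of result |
| Screening Visit | No | Eligibility criteria assessed |
| Visit 1 | No | Questionnaires after enrollment |
| Visit 2 | No | Verification of laboratory results; pregnancy counseling |
| Visit 3 | No | First dispensing |
| Visits 4 to 8 | No | Compliance checks and treatment monitoring |

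Total: one listing at baseline and none from the Screening Visit to the end of treatment.

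**2. Ask whether any other listed step forces a current result.**

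- *Exclusion criterion 3.* The wording refers to an office test, and the criteria are assessed at screening, so a test in clinic is likely then. It is not scheduled, and Visits 1 and 2 still come between it and the first dose.
- *Missing laboratory tests at Outside In.* A negative result already on file is not missing, however old it is. This provision fills gaps but does not refresh results.
- *Visit 2 verification.* The items named are blood count, INR, metabolic profile, GFR, genotype, HCV RNA and resistance variants. The list is introduced as non-exhaustive, so pregnancy could be checked here, but it is not named.
- *Visit 2 counseling.* This is advice, not a test.
- *Panel approval.* The panel supervises treatment initiation, but no current negative pregnancy test is stated as a condition of its approval.

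None of the five requires a negative result that is current at first dosing.

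**3. Ask how long the interval is.** No spacing is given between baseline testing, screening and Visits 1, 2 and 3, so the interval cannot be calculated. It may be short if the visits run close together. It may be longer where readiness is judged prospectively over several office visits (inclusion criterion 3), or where the baseline test predates screening.

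**4. Bound the number of subjects.** The prospective cohorts are 25 at each of two sites, so at most 25 + 25 = 50 subjects. The sex split is not given, so the number of childbearing potential lies between 0 and 50.

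**The case against.** The strongest reply is that the safeguards are layered and that a bulleted visit list is not the whole plan. Pregnant women are barred outright. The exclusion criterion implies a test in clinic. The already-done heading is not literal, since resistance testing appears both at baseline and at the Screening Visit. Counseling comes at the visit before dispensing, and a provider panel must approve the start of treatment. Several documents that the protocol refers to were not supplied: the safety monitoring plan (Section 10), the data sheets for each visit (Section 7c), the data collection and consent forms (Section 7a) and the prescriber information (Section 10, Drugs or Devices). A check before dispensing could naturally sit in any of them. The treatment risks in Section 9 also mention no reproductive harm, so the weight of the point rests on one sentence in Section 5c.

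Much of this stands. It makes dosing in pregnancy unlikely, and the gap may prove to be only a missing cross-reference. It does not supply a dated test before the first dose. The resistance-testing example also cuts the other way: where the protocol wants a baseline item addressed at screening, it lists it there, and pregnancy is not listed.

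Three stronger readings are tempting, and the documents do not support them.

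- *That the trial relies on a historical test alone.* The office-based wording of the exclusion and the screening assessment point to a likely test in clinic.
- *That the gap can be measured in weeks from the stated total duration.* That duration is approximate and is not a screening window.
- *That the primary analysis is threatened.* Nothing here bears on sample size or power, or calls for a change to the intention-to-treat SVR12 endpoint.

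**Conclusion.** The point holds as a gap in the listed safety steps. The protocol calls the drug contraindicated in pregnancy, yet the visit scheme does not require a current negative test before the first dose. The existing safeguards narrow the gap without closing it. The sponsor should correct it because the remedy is cheap and the risk preventable.

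The size is bounded only loosely: between 0 and 50 subjects, over an interval the protocol does not state. Confidence is medium. The conclusion assumes that the documents not supplied contain no such check, and it takes the contraindication as the protocol states it, since the label was not available for comparison.

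**What to change.** Add to Visit 3, before dispensing:

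> Office-based pregnancy test for subjects of childbearing potential; dispense only if negative; a subject who tests positive is not dosed and is linked to appropriate care.

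The care route can follow the one the Screening Visit already provides: "Screen failure subjects will be linked to appropriate care within the study site". A subject found pregnant at Visit 3 is already enrolled, however, so she should be recorded as enrolled but not dosed. Leave the intention-to-treat primary endpoint unchanged and report the number of such subjects. If the safety monitoring plan or the visit data sheets already require the test, a reference to that document at Visit 3 is enough.

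The cost is at most 50 office tests, up to 25 per site, at a visit that already takes place. A few enrolled subjects may go undosed.

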The results of this study will give insight into the feasibility of using safety net medical sites such as needle exchange programs and community health centers serving low income or homeless populations to safely and effectively treat this vulnerable population that is disproportionately affected by HCV infection. Furthermore, feedback from clients/patients using validated questionnaires could identify modifiable barriers to treatment success. Findings from this study could help expand the HCV treatment capacity beyond subspecialty practice and even the traditional primary care clinic.

4. Study Design

Study Objectives

Primary Objective: Determine if the clinical effectiveness of Zepatier in treating patients with HCV infection and mild fibrosis in two safety net sites, which offer comprehensive services to normalize the chaotic lifestyles of people who inject drugs and the homeless, is similar to what is expected in a tertiary hepatology clinic that cares for a more traditional patient population.

Secondary Objective: Identify client/patient factors that impact HCV treatment success in this population

Study Endpoints

Primary Endpoint

- Sustained virologic response rates measured at 12 weeks post treatment (SVR12)-Intention to Treat analysis (taking into account treatment discontinuation and failure rates)
- Persistently HCV infection free after 48 weeks of treatment cessation (SVR48)

Secondary Endpoints

- Adherence determined by client/subject self-reported medication adherence measured by percentage of pills taken on a monthly basis, as well as compliance with laboratory testing

- Treatment discontinuation rates including loss to follow up
- Percent of genotype 1a patients with baseline NS5A resistance

Relapse with substance use disorder in Old Town Clinic setting

Exploratory analysis of potential client/subject factors impacting readiness for treatment, non-adherence, or reinfection based on questionnaires administered at baseline and at 48 weeks post treatment

Study Design

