Outside In. Upon the study initiation, Outside In's Injection Drug Users Health Services Program will begin handing out fliers to all clients of the syringe exchange program as well as posting fliers on the bulletin board in the waiting room. These fliers will read, "Are you Hepatitis C Positive? Are you interested in treatment? Outside In is part of a study working to treat people with HCV. For more information and to see if you qualify for this study, please call 503-535-XXXX". This outreach process will be augmented with a respondent-driven sampling method called "snowball sampling," which uses social networks to find more clients in hard to reach populations. Representative seed subjects will be given

three coupons (fliers) to be given to other syringe exchange clients who also might be treatment candidates. Subjects may also be referred to study by their Outside In primary care provider. The phone line will be answered by the site coordinator and will have a voicemail that says “Thank you for your interest in our study. For this study, you need to be a current injection drug user. You must be over the age of 18. Please leave a name and a phone number you can be reached at. All calls will be returned the morning of the next business day. Thank you for your interest.” The site study coordinator will return the client’s call (two attempts will be made). This staff will confirm the initial screening conditions, inquire about insurance status, and make a medical appointment if appropriate. If the client is uninsured, he/she will be directed to OHP (Oregon Medicaid) enrollment and asked to re-engage with the study when insurance is active. If the client is insured by OHP, an appointment will be made for the client to meet with a treating medical provider. The provider appointment will serve as a medical screening visit to include missing baseline lab testing necessary to determine eligibility, the results of which will be helpful in determining inclusion. The first 25 patients that agree to be screened, meet criteria, and sign an informed consent to enroll in the study will be enrolled. Subjects will be reimbursed for each survey or in-depth interview with a \$15 Fred Meyer gift card.

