OHSU (Retrospective). The OHSU principle investigator, or IRB approved surrogate, will review the hepatology clinic Electronic Medical Record for patients treated for hepatitis C with Zepatier and select subjects in a retrospective, sequential fashion, starting at the time of closure of enrollment at the two prospective sites.

f. Consent Process

The consent coordinator will obtain consent during the intake appointment, after the initial screening process as detailed below. The consent coordinator will be an IRB-approved, OHSU affiliated employee of the study site, with 50% of their FTE covered by grant funding. This will occur in person, in a confidential clinic exam room, with ample time for questions and clarifications. The consent form will also be provided prior to the appointment so subjects have time to read over it and highlight any questions or concerns they may have. Subjects with low self-reported reading literacy will have the consent form read to them with a teach-back to confirm understanding. While all study coordinators will be employees of their parent organizations and will have access to the medical record, they will not be medical providers with a long standing relationships with the subjects to minimize potential for coercion and conflicts of interest.

For the purposes of this pilot study, only subjects who identify as proficient in the English language will be enrolled. The scientific rationale for this is based on a lack of validated non-English language questionnaires suiting our study question. In addition, the Medication Assisted Therapy population at the Old Town Clinic site of Central City Concern has only English speaking drug and alcohol counseling groups (present in East-Side Clinic, not participating in our study), potentially creating bias if non-English speaking patients were enrolled at the Outside In site.

Consent will follow a clinic visit with a study provider, who will use a basic capacity assessment to determine eligibility to consent. This will include the following general principles of being able to understand, express a choice, appreciation, and reasoning.⁹

6. Procedures Involved

- The primary therapeutic intervention will be one tablet of Zepatier (elbasvir 50mg/grazoprevir 100mg) daily with or without food for 12 weeks. This dosage is consistent with current FDA approval for the treatment of hepatitis C.

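### The intention-to-treat denominator for SVR12 is undefined: safety-net subjects are enrolled at consent and OHSU subjects are selected on treatment, so the two differ unless both are counted from first dose

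*Combined protocol and SAP*

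**What the plan says.** **Safety-net entry.** Section 5e uses the same sentence for Old Town Clinic and Outside In: "The first 25 patients that agree to be screened, meet criteria, and sign an informed consent to enroll in the study will be enrolled". In section 6 (Treatment Scheme), consent, eligibility, resistance testing and readiness belong to the Screening Visit. Visit 1 opens with "Once enrolled, completion of validated questionnaires". Visit 2 contains "Verify the following studies/assessments are complete including CBC" and "Verify Readiness for treatment". Drug is first dispensed at "Visit 3 (Initiation of HCV treatment").

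**OHSU entry.** Section 5e (and 5b) has the investigator search the hepatology record for "patients treated for hepatitis C with Zepatier and select subjects in a retrospective, sequential fashion". Treatment is the condition for entry.

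**Analysis set.** Section 4 (Study Endpoints) labels SVR12 "Intention to Treat analysis (taking into account treatment discontinuation and failure rates"). Section 8 names a chi-squared test and no analysis population. Two places hint at a denominator, in different directions. Section 8 (Power/Sample Size) counts 50 subjects enrolled, a number chosen to absorb 10% attrition. Section 4 (Study Design) describes 25 subjects per site as receiving Zepatier.

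**The concern.** A safety-net subject can be enrolled and never take a tablet. An OHSU subject cannot, because anyone lost between work-up and first fill is invisible to the record search. In its ordinary sense, intention to treat would keep the first kind of subject in the denominator as a failure. Pre-treatment loss would then lower SVR12 in one cohort only, and part of any deficit would reflect how the cohorts were assembled and not how well treatment worked.

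The study aims to show that safety-net cure rates are similar to those of a hepatology clinic, so an artefact in this direction works against its own hypothesis. The opposite choice also has a cost. If never-starters are dropped without a stated rule, a loss that is itself a barrier to care goes unreported. With no rule in the protocol, the choice could also be made after the results are known.

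**Working it through.** **1. Order of events (section 6).** Screening Visit (consent, criteria, resistance, readiness) → Visit 1 (questionnaires) → Visit 2 (verification) → Visit 3 (first drug). Visits 1 and 2 lie between consent and drug at the safety-net sites. The OHSU cohort has no such interval, because its members are found by having been treated.

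**2. Do the definitions settle the denominator?** Section 4 (Study Definitions) ties primary failure to detectable RNA 12 weeks after treatment, and discontinuation to therapy that was interrupted. Neither covers a subject who never started, so the denominator stays open.

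**3. The plan's own power figure.** Inputs from section 8: 50 per group, a 20-point difference, comparator 95%. Two-sided 5% is my assumption; the plan states no level. Normal approximation:

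power = Φ[(|p1 − p2| − 1.96·s0)/s1], where s0 is the pooled and s1 the unpooled standard error.

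- 95% vs 75%, 50 vs 50: s0 = 0.0714, s1 = 0.0686, so Φ[(0.20 − 0.140)/0.0686] = 80.9%. This reproduces the stated 80%.
- 95% vs 70%, the rates actually printed: 92.0%. The 20-point difference and the printed rates disagree. That is a separate matter, and this point does not depend on it.

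**4. Size of the artefact if all enrolled are counted.** Assume SVR12 among starters is 95% in both cohorts (the plan's OHSU figure), and that a fraction f of the 50 enrolled safety-net subjects never start and count as failures. The protocol gives no value for f.

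Observed safety-net SVR12 = 0.95 × (1 − f)

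- f = 5%: 0.95 × 0.95 = 90.3%, a gap of 4.75 points.
- f = 10%: 0.95 × 0.90 = 85.5%, a gap of 9.5 points.

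Chance of a significant result, by exact enumeration of two binomials (n = 50 each, OHSU at 95%, statistic above 3.84):

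| f | Uncorrected chi-squared | Yates-corrected |
|---|---|---|
| 0 | 4.3% | 0.7% |
| 5% | 13.5% | 5.8% |
| 10% | 36.5% | 22.0% |

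The protocol does not say which form of the test applies. The only loss figure it offers is the 10% allowance in section 8, which covers all attrition and loss to follow-up. The f = 10% row therefore assumes that the whole allowance is used up before first dose.

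**5. Counting from first dose.** Under the same assumption both cohorts sit at 95% and the gap is zero. The cost is sample size. With 10% never starting (45 vs 50), power for 95% vs 75% is Φ[(0.20 − 1.96 × 0.0723)/0.0715] = 79.3%.

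**The case against.** **Visit 2 is not the eligibility gate.** A reader might infer that subjects are enrolled first and checked for readiness and laboratory eligibility afterwards. The documents do not support that. The enrolment sentence requires that criteria be met. Readiness is an inclusion criterion and is also assessed at the Screening Visit. That visit includes "NS5A resistance testing for genotype 1a subjects (subjects excluded if baseline resistance present"), and the Outside In screening appointment fills in missing baseline laboratory tests. Visit 2 re-verifies. This part of the objection stands, and it leaves drop-out between consent and Visit 3 as the main route of loss, among people already selected for attendance and a wish to be treated.

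**The denominators may match.** Section 4 describes the safety-net subjects as receiving drug, and its gloss on intention to treat concerns events on treatment. On that reading both cohorts are counted from treatment and the bias is nil. This also stands, so a flat statement that the denominators are not comparable goes too far. It does not remove the problem, because the enrolled count in section 8 and the usual meaning of intention to treat point the other way.

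**Larger effects are speculative.** With f = 20% the same arithmetic gives 76.0% against 95% and false significance in 82% (uncorrected) or 71% (Yates) of trials. That rate is twice the plan's whole attrition allowance, and nothing in the documents makes it a planning scenario.

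**Counting from enrolment could be a legitimate estimand** when care models are compared. In principle that is right. It would need OHSU patients identified at a matching point before treatment, and selecting them on treatment rules that out.

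**Conclusion.** The point holds conditionally. The entry points differ as a matter of record, and the analysis set is undefined. If all enrolled subjects are counted, the primary comparison is biased against the safety-net clinics: by about 5 points if 5% never start and 9.5 points if 10% do, with false-significance rates of 14% and 36% (uncorrected) or 6% and 22% (Yates). These figures rest on assumed non-start rates, equal 95% SVR12 among starters and a two-sided 5% level. If both cohorts are counted from first dose, this source of bias disappears. Because the bias depends on an unstated choice and no non-start rate is documented, this is a should-fix, not a fatal flaw.

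**What to change.** Define the primary SVR12 set identically in all cohorts: every subject who received at least one dose of Zepatier, with all starters kept in the denominator and a missing SVR12 counted as failure. At the safety-net sites the count starts at Visit 3; at OHSU it starts at the first fill. Replace the bare intention-to-treat label with this definition.

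Report separately the number and proportion of safety-net subjects enrolled but never started, with reasons. Give SVR12 over all enrolled safety-net subjects as a descriptive supplementary figure, not tested against OHSU.

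The cost is protocol wording only. The safety-net denominator may fall slightly below 50; at 45 vs 50, power for 95% vs 75% is about 79% instead of 81%. If everyone enrolled starts treatment, the denominator stays at 50.
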